7.4. Dosage Modification

Not applicable.

7.5. Preparation/Handling/Storage/Accountability

Investigational products will be supplied by Lilly or its representative, in accordance with current Good Manufacturing Practices, and will be supplied with lot numbers, expiry dates, and certificates of analysis, as applicable.

Investigational product will be stored refrigerated (2°C to 8°C; 36°F to 46°F) in its original carton to protect from light. Investigational product should not be frozen or shaken.

Sites will be required to monitor temperature of the on-site storage conditions of investigational products.

7.6. Treatment Compliance

Every attempt will be made to select patients who have the ability to understand and comply with study instructions. The investigator is responsible for discussing methods to ensure high treatment compliance with the patient before randomization.

Randomized patients will record the date and time of administration of investigational product in a Study Drug Administration Log throughout their participation in the study. The data from the Study Drug Administration Log must be transcribed into the eCRF by site personnel.

Patient compliance with study medication will be assessed at each visit. Compliance will be assessed by review of the Study Drug Administration Log, return of empty investigational product packaging, and/or direct questioning.

The patient should be instructed to retain all empty study drug packaging after using up the medication and to bring the empty packaging and any unused medication to the study site at each visit, so that the site staff can record the amount of medication used since the last visit. Deviation(s) from the prescribed dosage regimen should be documented.

If a patient is noncompliant with study procedures and/or study drug administration, the investigator should assess the patient to determine the reason for noncompliance and educate and/or manage the patient as appropriate to improve compliance. If, in consultation with Lilly or its designee, the noncompliance is deemed to be significant or if further noncompliance occurs, the patient should be discontinued from the study (see Section 10.3.2.4 Treatment Compliance).

In some circumstances, it may be necessary to temporarily interrupt treatment (see Section 8.1.2 and Section 9.4.5). Any necessary interruption of treatment should be considered when determining noncompliance.

7.7. Concomitant Therapy

All concomitant medication taken during the study must be recorded on the Concomitant Medication case report form (eCRF) at the study visits indicated in the Schedule of Activities (Section 2). Treatment with concomitant PsA therapies during the study will be permitted only as outlined in the inclusion and exclusion criteria (Sections 6.1 and 6.2, respectively) and as described below. Patients taking permitted PsA medications should be on stable doses at randomization (Visit 2) and through the first 24 weeks of the Open-Label Treatment Period, as specified below, unless changes are required for safety reasons. Table RHCF.7.2, Table RHCF.7.3, and Table RHCF.7.4 summarize concomitant medications that are and are not permitted and the conditions for use during the study for those which are permitted.

Table RHCF.7.2. Concomitant Medications Permitted/Not Permitted in the Open-Label Treatment Period from Week 0 to Week 24 for Treatment of PsA and Chronic Conditions

Drug Class	As Needed	Chronic Use	Conditions for Use
bDMARDs	N	N	Not allowed
PDE4 or JAK inhibitors	N	N	Not allowed
csDMARDs	N	Y	Stable dose allowed. Stable doses with no dose adjustments, changes, and/or introduction of a new csDMARD Allowed doses: Oral or parenteral MTX; 10 to 25 mg/week Leflunomide: up to 20 mg/day Sulfasalazine: up to 3 g/day Cyclosporine: up to 5 mg/kg/day
Live vaccines (including BCG)	N	N	Not allowed
Phototherapy	N	N	Not allowed

Drug Class	As Needed	Chronic Use	Conditions for Use
NSAIDs, COX-2			Stable doses with no dose adjustments, changes,
inhibitors			and/or introduction of a new NSAID.
	N	Y	Allowed up to the maximum recommended doses
	11	1	for pain.
			Aspirin (doses not exceeding 350 mg/day) may
			be taken to manage cardiovascular risk.
Opiate analgesics			Stable doses with no dose adjustments, changes,
	N	Y	and/or introduction of a new opiate analgesic.
	1	_	May be used at average daily doses ≤30 mg/day
			of morphine or its equivalent
Nonopiod analgesics			Allowed up to the maximum recommended doses
(paracetamol and			for pain.
acetaminophen)			May be administered as needed basis during the
	Y	Y	study, but should be withheld within 24 hours of
			a visit.
			May be used at doses ≤1000 mg for
			premedication for allergic/hypersensitivity
			reactions from injections (see Section 7.8.3)
Topical steroids			Weak potency (WHO Group 1 classification
	Y	Y	only as needed, but not within 24 hours of PASI
			assessment
Oral corticosteroids			Stable doses with no dose adjustments, changes,
	N.T.	37	and/or introduction of a new oral corticosteroid
	N	Y	Allowed doses:
			≤ an average daily dose of 10 mg/day of
T			prednisone or equivalent)
Intravascular and IM	N	N	Not allowed
glucocorticoid			N.411 1
Intra-articular	N	N	Not allowed
glucocorticoid Inhaled steroids	Y	Y	As needed or regular use for asthma is permitted
Nasal corticosteroids	Y	Y	Use for allergies is permitted
	I	ĭ	9 1
Medicated shampoos			Shampoos that do not contain >3% salicylic acid,
Tonical			corticosteroids, coal tar, or vitamin D3 analogs
Topical moisturizers/emollients			Topical moisturizers/emollients and other
and other			nonprescription topical products that do not
nonprescription topical			contain, urea, >3% salicylic acid, alpha- or beta-
products	Y	Y	hydroxyl acids, corticosteroids, or vitamin D3
products	I	I	analogs
Bath oils and oatmeal			anarogs
bath preparations			Allowed
			These topical therapies are not to be used within
			12 hours prior to a study visit

Abbreviations: BCG = Bacillus Calmette-Guérin; bDMARD = biological disease-modifying anti-rheumatic drugs; COX-2 = cyclooxygenase-2; csDMARD = conventional synthetic disease-modifying anti-rheumatic drugs; IM = intramuscular; JAK = Janus kinase; MTX = methotrexate; N = No; NSAID = nonsteroidal anti-inflammatory drug; PASI = Psoriasis Area and Severity Index; PDE4 = phosphodiesterase type 4; Y = Yes; WHO = World Health Organization.

Table RHCF.7.3. Concomitant Medications Permitted/Not Permitted in the Open-Label Treatment Period from Week 24 to Week 52 for Treatment of PsA and Chronic Conditions

Drug Class	As Needed	Chronic Use	Conditions for Use
bDMARDs	N	N	Not allowed
PDE4 or JAK inhibitors	N	N	Not allowed
csDMARDs	N	Y	Allowed doses: Oral or parenteral MTX; 10 to 25 mg/week Leflunomide: up to 20 mg/day Sulfasalazine: up to 3 g/day Cyclosporine: up to 5 mg/kg/day
Live vaccines (including BCG)	N	N	Not allowed
Phototherapy	N	N	Not allowed
NSAIDs, COX-2 inhibitors	Y	Y	Allowed up to the maximum recommended doses for pain. Aspirin (doses not exceeding 350 mg/day) may be taken to manage cardiovascular risk.
Opiate analgesics	Y	Y	Allowed
Nonopiod analgesics (paracetamol and acetaminophen)	Y	Y	Allowed up to the maximum recommended doses for pain. May be administered as needed basis during the study, but should be withheld within 24 hours of a visit. May be used at doses ≤1000 mg for premedication for allergic/hypersensitivity reactions from injections (see Section 7.8.3)
Topical steroids	Y	Y	Allowed as needed, but not within 24 hours of PASI assessment
Oral corticosteroids	Y	Y	Allowed doses: ≤ an average daily dose of 10 mg/day of prednisone or equivalent)
Intravascular and IM glucocorticoid	N	N	Not allowed
Intra-articular glucocorticoid	N	N	Allowed on a limited basis: it is recommended that there be no more than 1 injection (one injection = one large joint or up to 5 small joints or one soft tissue)
Inhaled steroids	Y	Y	As needed or regular use for asthma is permitted
Nasal corticosteroids	Y	Y	Use for allergies is permitted

Drug Class	As Needed	Chronic Use	Conditions for Use
Medicated shampoos			Allowed
Topical moisturizers/emollients and other nonprescription topical products	Y	Y	Topical moisturizers/emollients and other nonprescription topical products that do not contain, urea, >3% salicylic acid, alpha- or betahydroxyl acids, corticosteroids, or vitamin D3 analogs
Bath oils and oatmeal bath preparations			Allowed
oam preparations			These topical therapies are not to be used within 12 hours prior to a study visit

Abbreviations: BCG = Bacillus Calmette-Guérin; bDMARD = biological disease-modifying anti-rheumatic drugs; COX-2 = cyclooxygenase-2; csDMARD = conventional synthetic disease-modifying anti-rheumatic drugs; IM = intramuscular; JAK = Janus kinase; MTX = methotrexate; N = No; NSAID = nonsteroidal anti-inflammatory drug; PASI = Psoriasis Area and Severity Index; PDE4 = phosphodiesterase type 4; Y = Yes; WHO = World Health Organization.

Table RHCF.7.4. Allowed Concomitant Medications in the Post-Treatment Follow-Up Period (Period 3)

Drug Class	As Needed	Chronic Use	Conditions for Use
bDMARDs	Y	Y	Allowed Follow local guidance; at the discretion of investigator
PDE4 or JAK inhibitors	Y	Y	Allowed Follow local guidance; at the discretion of the investigator
csDMARDs	Y	Y	Allowed
Live vaccines (including BCG)	N	N	Not allowed
Phototherapy	Y	Y	Allowed
NSAIDs, COX-2 inhibitors	Y	Y	Allowed
Opiate analgesics	Y	Y	Allowed
Nonopiod analgesics (paracetamol and acetaminophen)	Y	Y	Allowed
Topical steroids	Y	Y	Allowed
Oral corticosteroids	Y	Y	Allowed
Intravascular and IM glucocorticoid	Y	Y	Allowed
Intra-articular glucocorticoid	Y	Y	Allowed
Inhaled steroids	Y	Y	As needed or regular use for asthma is permitted
Nasal corticosteroids	Y	Y	Use for allergies is permitted

Drug Class	As Needed	Chronic Use	Conditions for Use
Medicated shampoos			Allowed
Topical moisturizers/emollients and other nonprescription topical products	Y	Y	
Bath oils and oatmeal bath preparations			

Abbreviations: BCG = Bacillus Calmette-Guérin; bDMARDs = biological disease-modifying anti-rheumatic drugs; COX-2 = cyclooxygenase-2; csDMARD = conventional synthetic disease-modifying anti-rheumatic drugs; IM = intramuscular; JAK = Janus kinase; MTX = methotrexate; N = No; NSAID = nonsteroidal anti-inflammatory drug; PASI = Psoriasis Area and Severity Index; PDE4 = phosphodiesterase type 4; Y = Yes; WHO = World Health Organization.

To avoid any possible drug interactions for those patients randomized to adalimumab, please refer to the product labeling for adalimumab for further concomitant therapy restrictions.

Additional drugs are to be avoided during the study unless required to treat an AE or for the treatment of an ongoing medical problem. If the need for concomitant medication arises, the investigator should base decisions on the patient and clinical factors.

Patients should be instructed to consult the investigator or other appropriate study personnel at the site before taking any new medications or supplements. Any changes in medications not addressed above should be discussed by the investigator with the sponsor.

7.8. Treatment after the End of the Study

7.8.1. Study Extensions

Not applicable.

7.8.2. Continued Access

Investigational product will not be made available to patients after the conclusion of the study.

7.8.3. Special Treatment Considerations

All biological agents carry the risk of systemic allergic/hypersensitivity reactions. Clinical manifestations of these reactions may include, but are not limited to:

- skin rash
- pruritus (itching)
- urticaria (hives)
- angioedema (eg, swelling of the lips and/or tongue)
- anaphylactic reaction

Sometimes these reactions can be life-threatening. Proteins may also cause redness, itching, swelling, or pain locally at the injection site. Therefore, all patients should be closely monitored for signs or symptoms that could result from such reactions, be educated on the signs or symptoms of these types of reactions, and be instructed to contact the study site immediately if any of the symptoms are experienced after an injection. If a patient experiences an acute allergic/hypersensitivity reaction after an injection of investigational product, he or she should be managed appropriately and given instruction to receive relevant supportive care.

For patients who experience a potential allergic/hypersensitivity reaction, consideration for any premedication for future injections will be agreed upon between the investigator and sponsor and/or its designee. Examples of potential allergic/hypersensitivity reactions that might merit premedication include mild-to-moderate skin rashes, mild-to-moderate generalized pruritus and/or urticaria, and mild-to-moderate injection-site reactions (eg, injection-site erythema, injection-site pruritus). Patients who develop clinically significant systemic allergic/hypersensitivity reactions after administration of investigational product who do not respond to symptomatic medication or result in clinical sequelae should be discontinued from study treatment and not receive further doses of investigational product, with or without premedication (see Section 8). Medications considered appropriate for premedication include (but are not restricted to) acetaminophen/paracetamol up to 1000 mg and antihistamines (eg, oral diphenhydramine, 50 mg) given 30 to 60 minutes before investigational product injection. Patients may self-premedicate at home before administration of investigational product, as directed by the investigator. All such premedications will be recorded as concomitant therapy. Corticosteroids are not permitted as agents for premedication.

8. Discontinuation Criteria

8.1. Discontinuation from Study Treatment

8.1.1. Permanent Discontinuation from Study Treatment

Discontinuation of the investigational product for abnormal liver tests **should be considered** by the investigator when a patient meets one of the following conditions after consultation with the Lilly-designated medical monitor:

- alanine aminotransferase (ALT) or aspartate aminotransferase (AST) >8X upper limit of normal (ULN)
- alanine aminotransferase or AST >5X ULN for more than 2 weeks
- alanine aminotransferase or AST >3X ULN and total bilirubin level (TBL)
 >2X ULN or prothrombin time >1.5X ULN
- alanine aminotransferase or AST >3X ULN with the appearance of fatigue, nausea, vomiting, right upper-quadrant pain or tenderness, fever, rash, and/or eosinophilia (>5%)
- alkaline phosphatase (ALP) >3X ULN
- alkaline phosphatase >2.5X ULN and TBL >2X ULN
- alkaline phosphatase >2.5X ULN with the appearance of fatigue, nausea, vomiting, right quadrant pain or tenderness, fever, rash, and/or eosinophilia (>5%)

In addition, patients will be discontinued from the investigational product in the following circumstances:

- Neutrophil (segmented) counts (see Section 9.4.5.3 for information on monitoring for neutropenia)
 - o <500 cells/uL
 - ≥500 and <1000 cells/uL (based on 2 test results; the second test performed within 1 week from knowledge of the initial result).
 - ≥1000 and <1500 cells/uL (based on 3 test results) and an infection that is not fully resolved.
 

- Total white blood cell count <2000 cells/μL.
- Lymphocyte count <500 cells/μL.
- Platelet count <50,000 cells/μL.
- Changes in blood pressure defined as sitting systolic blood pressure at ≥160 mm Hg plus ≥20 mm Hg increase from baseline (Visit 2 [Week 0]), and/or diastolic blood pressure at ≥100 mm Hg plus ≥10 mm Hg increase from baseline, that do not respond following maximal allowed intervention (see Section 9.4.5.1 for information on monitoring hypertension).

- The patient experiences a severe AE, an SAE, or a clinically significant change in a laboratory value occurs that, in the opinion of the investigator, merits the discontinuation of the investigational product and appropriate measures being taken. In this case, Lilly or its designee is to be notified immediately.
- Clinically significant systemic hypersensitivity reaction after SC administration of investigational product that does not respond to symptomatic medication or results in clinical sequelae.
- The patient becomes pregnant.
- The patient develops a malignancy. **Note**: Patients may be allowed to continue if they develop no more than 2 nonmelanoma skin cancers over any 12-month period during the study.
- The patient develops symptoms suggestive of a lupus-like syndrome and is positive for antibodies against double-stranded DNA.
- If the patient, for any reason, requires treatment with another therapeutic agent that has been demonstrated to be effective for the treatment of PsA or Ps, discontinuation from the study occurs prior to introduction of the new agent.
- Enrollment in any other clinical trial involving an investigational product or enrollment in any other type of medical research judged not to be scientifically or medically compatible with this study.
- The patient develops active suicidal ideation with some intent to act with or without a specific plan (yes to question 4 or 5 on the "Suicidal Ideation" portion of the C-SSRS) or develops suicide-related behaviors as recorded on the C-SSRS. It is recommended that the subject be assessed by a psychiatrist or appropriately trained professional to assist in deciding whether the subject is to be discontinued from the study.
- The patient develops any condition or contraindication as addressed in the local labelling for adalimumab that would preclude the patient from continuing in this protocol.
- The investigator or attending physician decides that the patient should be withdrawn from the study.
- The patient requests to be withdrawn from the study.
- The investigator or Lilly stops the patient's participation in the study or Lilly stops the study for medical, safety, regulatory, or other reasons consistent with applicable laws, regulations, and good clinical practice (GCP).
- The patient becomes HBV DNA positive. The patient should be referred to a specialist physician.
- The patient is diagnosed with an active TB infection.

If in consultation with Lilly or its designee noncompliance is deemed to be significant or if further noncompliance occurs, the patient may be discontinued from the study (see Section 10.3.2.4 Treatment Compliance).

Any patient who permanently discontinues the study treatment for any reason will stop treatment and continue to the ETV prior to entering the Post-Treatment Follow-Up Period (Period 3).

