9.4.5.3. Neutropenia

Patients with neutrophil counts <1500 cells/μL should be managed for neutropenia as follows:

- <500 cells/µL, see Discontinuation Criteria (Section 8.1.1)
- \geq 500 cells/ μ L and <1000 cells/ μ L, see Discontinuation Criteria (Section 8.1.1)
- ≥1000 cells/μL and <1500 cells/μL (based on 3 test results), and the patient has a concurrent infection that requires systemic anti-infective therapy (for example, antibiotic, antifungal agent, antiviral agent):
 - The dose of investigational product should be withheld, the patient should receive appropriate medical care, and a repeat test for neutrophil count should be performed within 4 weeks from knowledge of the initial report. If the repeat neutrophil count has returned to $\geq\!1500$ cells/µL and the infection has resolved or is resolving, the patient may resume dosing of investigational product and evaluation at scheduled visits. If the neutrophil count remains $\geq\!1000$ cells/µL and $<\!1500$ cells/µL, investigational product should continue to be withheld and a repeat neutrophil count should again be performed within another 4 weeks. If, after 2 repeat tests, the neutrophil count still remains $\geq\!1000$ cells/µL and $<\!1500$ cells/µL, and:
 - a. the infection has not fully resolved, the patient will be discontinued from the study.
 - b. the infection has resolved, the patient may resume dosing and evaluation at scheduled visits. However, if resumption of dosing is not deemed appropriate by the investigator, the patient will be discontinued from the study.
- ≥1000 cells/μL and <1500 cells/μL (based on 3 test results), and the patient has no concurrent infection that requires systemic anti-infective therapy (for example, antibiotic, antifungal agent, antiviral agent):

 Dosing may continue, and a repeat neutrophil count should be performed 4 to 8 weeks from knowledge of the initial report. Testing may be at a regularly scheduled visit or at an unscheduled visit, as necessary.

Repeat testing should be performed at 4- to 8-week intervals until the neutrophil count has returned to $\geq\!1500$ cells/ μL . If the patient has 3 or more postbaseline neutrophil counts of $\geq\!1000$ cells/ μL and $<\!1500$ cells/ μL , no value of $<\!1000$ cells/ μL , and no postbaseline infection requiring systemic anti-infective therapy, the patient may continue or resume further evaluation at scheduled visits, as deemed appropriate by the investigator.

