Important Protocol Violation Category/Subcategory	Source to Identify Protocol Violation	Statistical Programming Guidance for Clinical Study Report
[48] Are currently enrolled in, or discontinued from a clinical trial involving an investigational product or nonapproved use of a drug or device within the last 4 weeks or a period of at least 5 half-lives of the last administration of the drug, whichever is longer, or are concurrently enrolled in any other type of medical research judged not to be scientifically or medically compatible with this study.	Monitor	Monitor's list
[49] Are unwilling or unable to comply with the use of a data collection device to directly record data from the patient.	Monitor	Monitor's list
Category: Study Procedures		
Sub-Category: Violation of Discontinuation Criteria		
[D1] Discontinuation of the study drug after consultation with medical monitor for abnormal liver tests, defined as having 1 of the following: ALT or AST >8× ULN ALT or AST >5× ULN for more than 2 weeks ALT or AST >3× ULN and total bilirubin level >2× ULN or prothrombin time >1.5× ULN ALT or AST >3×ULN with the appearance of fatigue, nausea, vomiting, right upper-quadrant pain or tenderness, fever, rash, and/or eosinophilia (>5%) ALP >3× ULN ALP >2.5× ULN and TBL >2× ULN ALP >2.5× ULN with the appearance of fatigue, nausea, vomiting, right quadrant pain or tenderness, fever, rash, and/or eosinophilia (>5%)	Monitor	Monitor's list

Important Protocol Violation Category/Subcategory	Source to Identify Protocol Violation	Statistical Programming Guidance for Clinical Study Report
[D2] Neutrophil (segmented) counts: <500 cells/ μ L; or \geq 500 and <1000 cells/ μ L (from 2 test results; the second test must be performed within 1 week from knowledge of the initial result); or \geq 1000 and <1500 cells/ μ L (from 3 test results) and an infection that is not fully resolved	Monitor and Stats	Monitor’s list, or, If a patient still receives study treatment after 10 days of latest dose with confirmed segmented neutrophil counts <500 cells/ μ L; \geq 500 and <1000 cells/ μ L (from a test and a re-test result; the re-test must be performed within 1 week from knowledge of the initial result); or \geq 1000 and <1500 cells/ μ L (from a test and 2 re-test results) and an infection that is not fully resolved If there are missing re-test results, use the non-missing results

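### At a neutrophil count of 1000 to <1500 cells/µL, Protocol 8.1.1 and SAP item D2 count any unresolved infection towards a permanent stop, while Protocol 9.4.5.3 lets dosing go on unless the infection needs systemic treatment

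*Protocol*

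**What the plan says.** **Protocol 8.1.1.** The list of mandatory stops opens with "patients will be discontinued from the investigational product in the following circumstances". For 1000 to <1500 cells/µL the condition is "based on 3 test results) and an infection that is not fully resolved". It does not qualify the infection by type or by how it is treated. The pointer to the other section is "see Section 9.4.5.3 for information on monitoring for neutropenia".

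**Protocol 9.4.5.3, first branch.** The entry condition is the same count band, "based on 3 test results), and the patient has a concurrent infection that requires systemic anti-infective therapy". The action is "The dose of investigational product should be withheld, the patient should receive appropriate medical care". A repeat count is due within 4 weeks of the initial report, and another within a further 4 weeks if the count stays in the band. If it is still there after two repeats, the patient leaves the study if the infection is unresolved, and may resume dosing if it has resolved.

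**Protocol 9.4.5.3, second branch.** The band and the three results are the same, but "the patient has no concurrent infection that requires systemic anti-infective therapy". The action is "Dosing may continue, and a repeat neutrophil count should be performed 4 to 8 weeks from knowledge of the initial report".

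**SAP 6.17, Table RHCF.6.9, item D2.** For this band, the programmed check flags a patient who is still receiving treatment beyond a 10-day allowance when the count condition is met "from a test and 2 re-test results) and an infection that is not fully resolved". If re-tests are missing, the available results are used.

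**The concern.** The sections apply different tests to the same patient. Section 8.1.1 and D2 ask whether an infection is unresolved. Section 9.4.5.3 asks whether the infection needs systemic treatment. The same phrase about three results also appears at two different points: as the trigger for a permanent stop in 8.1.1, and as the trigger for withholding in 9.4.5.3.

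Three things depend on which text a site follows:

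- **Exposure.** Cytopenias and infections are both adverse events of special interest (Protocol 9.2.1.1), so this is a group in which continued dosing matters.
- **Efficacy data.** A permanent stop leads to the early termination visit and then to follow-up, where no efficacy assessments are scheduled. Missing response counts as nonresponse (SAP 6.4.1).
- **Violation status.** SAP 6.17 plans additional analyses of the primary and/or major secondary endpoints in patients without any, or without a subset of, violations. A D2 flag can therefore change who enters those analyses.

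**Working it through.** No sample size, power or error rate is involved, so the check compares the texts by infection status. It uses both readings of three test results: (A) three results are needed before the 9.4.5.3 branch begins; (B) the three are the initial test plus two repeats.

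| Infection status, count 1000 to <1500 on three results | 8.1.1 | 9.4.5.3, reading A | 9.4.5.3, reading B |
|---|---|---|---|
| None | Not triggered | Dosing allowed | Dosing allowed |
| Unresolved, systemic treatment not needed | Permanent stop | Dosing allowed | Dosing allowed |
| Unresolved, systemic treatment needed | Permanent stop | Withhold, two more tests, may resume | Withhold from the first low result; out after the third if unresolved |

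**Row 1.** There is no conflict.

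**Row 2.** The sections conflict under both readings, because the difference lies in the definition of the infection and not in the number of tests.

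**Row 3.** Reading A needs 3 + 2 = 5 results before a decision, against 3 in 8.1.1, so withholding would begin only when the stop condition already holds. Reading B needs 1 + 2 = 3 results, which agrees with 8.1.1. The three-result condition at the head of the branch is then in the wrong place. Three things favour reading B: the repeats are timed from the initial report, the decision follows two repeats, and D2 spells out one test and two re-tests.

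**Whether anything else settles row 2:**

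- The cross-reference in 8.1.1 is for monitoring only and sets no order of precedence.
- Section 9.4.5.3 sends the reader back to 8.1.1 for counts below 1000, but not for this band.
- Section 8.1.2 allows temporary interruption for neutropenia by pointing to 9.4.5.3, with no threshold of its own.
- Section 7.4 (dosage modification) gives no rule.
- Section 5.1.3 also uses the systemic-treatment criterion, but only for post-treatment follow-up.

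**What D2 would flag:**

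- A patient whose drug is withheld under the first branch is not receiving treatment, so the programmed check does not flag that patient.
- A row 2 patient dosed as 9.4.5.3 allows meets the unqualified condition and can be flagged.
- Because missing re-tests are replaced by whatever results exist, a patient could be flagged on fewer than the three results that 8.1.1 requires.

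**The case against.** The best defence is that 8.1.1 only summarises the endpoint of the first 9.4.5.3 branch. Both end treatment when the infection has not fully resolved, and on reading B both do so at the third result. This disposes of most of the stop-versus-withhold conflict and leaves a misplaced phrase.

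On that view the infection in 8.1.1 would also be the systemically treated one. That may be what was meant, but the reader has to supply it. Section 8.1.1 is mandatory, speaks of an infection without qualification, and cites 9.4.5.3 only for monitoring. D2 repeats the unqualified wording as a programming instruction. The mismatch in row 2 therefore stands.

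Some stronger inferences are tempting, and the documents do not support them:

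- **One patient could be stopped, withheld or dosed on.** Each affected patient faces two outcomes: stop or withhold with a systemically treated infection, stop or continue with another infection.
- **Months of dosing could pass before a third result, given the scheduled haematology visits.** Section 9.4.5.3 sets its own repeats (within 4 weeks, or every 4 to 8 weeks) and provides for unscheduled visits. Section 8.1.2 allows interruption in the meantime.
- **The stop falls weeks later under 9.4.5.3 than under 8.1.1.** On reading B the second repeat is the third result, so there is no delay.
- **Anyone managed under 9.4.5.3 becomes a violation.** The check requires continued treatment, so a withheld patient is not caught.
- **Handling will differ by arm.** Open-label treatment makes this possible, but the text is the same for both arms and nothing in the documents shows that it would happen.

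**Conclusion.** The inconsistency is real but narrow. For three counts of 1000 to <1500 cells/µL with an unresolved infection that does not need systemic treatment, 8.1.1 and 9.4.5.3 give opposite instructions on either reading of the three results. D2 sides with the 8.1.1 wording, so dosing that one section permits can be recorded as an important violation. The placement of the three-result phrase in 9.4.5.3 is a lesser drafting fault, and a true conflict only if read literally.

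The documents give no rate for this combination. That few patients will meet it is a judgement, and no material effect on the main efficacy results is claimed. An early stop does not automatically produce nonresponse at Week 24 either, because SAP 6.1 maps early-termination data to the next planned visit. The case for correction rests on patient safety and on consistent classification of violations. No view is taken on which clinical rule is right.

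**What to change.** Reconcile Protocol 8.1.1, Protocol 9.4.5.3 and SAP item D2:

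1. Use one definition of the qualifying infection in all three places.
2. State once what three test results means: the trigger for withholding, or the initial test plus the two repeats that lead to the discontinuation decision. Keep the phrase only where that meaning applies.
3. Align the D2 programming with the reconciled rule, including what happens when a re-test is missing.

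Which rule to adopt is for the sponsor. The cost is a wording clarification in two protocol sections and one SAP table row, plus the matching program change. No additional patients, tests or visits are needed.
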